2.3 Risk/Benefit Assessment

2.3.1 KNOWN POTENTIAL RISKS

The Medication risks:

Patients randomized to receive oral valganciclovir will be at risk of developing complications due to systemic toxicity. Although this drug is widely prescribed to treat CMV anterior uveitis in the United States, there are known adverse effects. Common ones include fever, headache, insomnia, diarrhea, nausea, vomiting, and abdominal pain. Rare side effects include hematologic abnormalities, acute renal failure, infertility, teratogenesis, and carcinogenesis. Patients randomized to receive topical ganciclovir eye drops will be subjected to the risks of topical toxicity. These include corneal epitheliopathy and conjunctivitis, both of which are almost always reversible upon discontinuation of the topical medication.

Minimizing medication risks:

Due to the potential complications associated with oral valganciclovir, patients will obtain pre-study labs, as well as monitoring labs throughout the study. The pre-study labs are to ascertain whether an individual is at greater risk of developing complications such as bone marrow suppression or acute renal failure. Patients identified as being high risk will be excluded from the study, as specified in our protocol. Patients enrolled in the study will receive regular laboratory tests in order to monitor CBC and renal function. Those that develop blood or renal abnormalities as specified in the protocol will be removed from the study. For patients that are randomized to receive topical antiviral therapy, the regular schedule of follow-up with clinical exam by a study ophthalmologist will provide ample opportunity to detect topical toxicity and discontinue medications as described in our protocol.

Procedural risks:

Although extremely rare, risks associated with anterior chamber paracentesis include endophthalmitis and traumatic cataract, both of which can lead to vision loss. In rare cases, endophthalmitis warrants need for eye removal.

Minimizing procedural risk:

All study ophthalmologists are trained to safely utilize anterior chamber paracentesis techniques to access fluid in the anterior chamber. Sterilization drops will be used in order to minimize the risks of intra-ocular infection.

2.3.2 KNOWN POTENTIAL BENEFITS

The benefits to the participant include a potential for a positive health outcome due to closer follow-up than standard care. Knowledge will be gained about their personal health through objective microbiological outcomes, which may help direct their care after study completion. Additionally, these participants will be contributing to work that could potentially guide treatment of CMV anterior uveitis for patients around the world. These benefits, in addition to the others mentioned above are reasonably balanced with the risks of partaking in the study.

2.3.3 ASSESSMENT OF POTENTIAL RISKS AND BENEFITS

Knowledge gained from this study may help improve the treatment of CMV anterior uveitis around the world. Given the risks to participants in this study, we feel the benefits of the important knowledge we expect to gain from this study outweigh the risks.

3 OBJECTIVES AND ENDPOINTS

OBJECTIVES	ENDPOINTS	JUSTIFICATION FOR ENDPOINTS
Primary		
Specific Aim 1: To compare CMV viral load and inflammation after randomization to oral valganciclovir, topical ganciclovir, or placebo.	Reduction in log transformed viral load as measured by quantitative PCR at 7 days of treatment.	Viral load post 7 days of treatment using fluid from the eye is an important micro biologic outcome to compare the effect of treatment. This is primary outcome for Trial I
Specific Aim 2: To compare the effect of long-term antiviral suppression on recurrence of inflammation.	Proportion of participants with recurrence at the end of 6months.	CMV recurrence is a clinical outcome indicating effect of long-term treatment in controlling inflammation and preventing recurrence. This is primary outcome for Trial II
Specific Aim 3: To determine if antiviral resistance mutations develop with exposure to long-term antiviral suppression.	Prevalence of mutations associated with antiviral resistance	Using aqueous fluid from the eye, comparing prevalence of mutations conferring antiviral resistance in at baseline (Trial I) and recurrent disease (Trial II) is important to determine the relationship between viral and host genome features that mediate inflammation in CMV anterior uveitis.

4 STUDY DESIGN

4.1 Overall Design

The Systemic and topical antiviral control of cytomegalovirus anterior uveitis: treatment outcomes (STACCATO) study will enroll participants with PCR-proven CMV anterior uveitis into a sequential double-masked randomized clinical trial in the US and Asia. In Trial I, participants will be randomized to one of the three treatment groups:

Group 1: Valganciclovir tablets 900 mg PO BID (4 tablets daily) and Placebo drops 1 drop 6 times daily

Group 2: Topical ganciclovir 2% 1 drops 6 times daily and Placebo tablets 2 tablets PO BID (4 tablets daily)

Group 3: Placebo tablets 2 tablets PO BID (4 tablets daily) and Placebo drops 1 drop 6 times daily

After participants achieve control of their inflammation, they will enter Trial II at which point they will be re-randomized to one of the three arms in Trial I at a prophylactic dosing. Additionally, patients with known CMV anterior uveitis, but who are inactive, may enter Trial II directly. Recurrences of inflammation in Trial II will be assessed for presence of detectable viral load. Those who agree to participate will be randomized at baseline and after achieving clinical quiescence, get re-randomized to one of the three treatment groups:

Group 1: Valganciclovir tablets 450 mg PO BID (2 tablets daily) and Placebo drops 1 drop BID

Group 2: Topical ganciclovir 2% 1 drop BID and Placebo tablets 1 tablet PO BID (2 tablets daily)

Group 3: Placebo tablets 1 tablet PO BID (2 tablets daily) and Placebo drops 1 drop BID

All study ophthalmologists and participants will remain masked to treatment assignment after enrollment. Due to the treatment design, all participants will receive both pills and eye drops. An interim analysis will be performed for both trials once primary outcome data is available for one third of the patients.

4.1.1 . STUDY MASKING PROCEDURES (EXAM #2 AND 3)

- The patient comes for the study visit and meets with the study coordinator before seeing their study doctor. This will facilitate masking of ophthalmologists and participants. All outcome assessors including lab technicians for trial I and ophthalmologists for trial II will remain masked. To facilitate interim and safety analysis, a data team member may also be unmasked.
- The patient's medication bottles are immediately placed in a secure, black bag and left at the study coordinators desk for the remainder of the visit. Patient medication calendars should also be placed in the black bag.
- The study coordinator will check-in with the patient and complete the following in any order:
 - Review of patient medication diaries
 - Review of adverse events since last visit*
 - Dispense new medication bottle (*if applicable*)

4.2 Scientific Rationale for Study Design

Randomized control trials are known to be the least biased form of evidence; we have chosen to do a randomized double- masked, placebo- controlled trial to reduce bias as much as possible.

4.3 End of Study Definition

A participant is considered to have completed the study if he or she has completed all visits and procedures and exams of the study described in Assessments and Procedures **Section 7.1**.

4.4 Adherence

Participants will be given a treatment diary in the form of a weekly calendar on which they will be asked to record adherence as well as reasons for missed doses. At each study visit, the study coordinator will review with the participant their treatment calendar, and document findings in the Medication Log in each participant file. Pill counting and medication bottle weighing will also be done for an objective measure of adherence. Participants who miss a scheduled dose of medication will be instructed to skip that dose and continue with their next scheduled dose of tablets or eye drops.

5 STUDY POPULATION

5.1 Inclusion Criteria

In order to be eligible to participate in Trial I of this study, an individual must meet all of the following criteria:

- CMV positivity by nucleic acid amplification test (e.g., polymerase chain reaction) from aqueous humor obtained via anterior chamber paracentesis obtained during an active flare of inflammation (uveitis) preceding enrollment into study
- Active anterior uveitis using Standardisation of Uveitis Nomenclature (SUN) Working group with clinical impression of CMV as the etiologic agent defined as $\geq 1+$ anterior chamber cell²¹
- Participant willingness to use an acceptable method of contraception during the study period (i.e., pharmacologic, barrier methods or abstinence).
- Age over 18 years
- Basic understanding of the study as determined by the physician
- Commitment to return for follow up visits

To be eligible for Trial II, an individual must:

- Have a history of being CMV positive by nucleic acid amplification test (e.g., polymerase chain reaction) from aqueous humor obtained via anterior chamber paracentesis during an active flare of inflammation (uveitis)
- Have inactive inflammation ($< 1+$ anterior chamber cell) for at least 2 weeks
- Have a period of 2 weeks of no antiviral prior to long-term treatment initiation

5.2 Exclusion Criteria

An individual who meets any of the following criteria will be excluded from participation in this study:

Trial I

- Negative for CMV by nucleic acid amplification test (e.g., polymerase chain reaction) of aqueous humor obtained via anterior chamber paracentesis during an active flare of inflammation (uveitis) preceding enrollment into study
- Participants <18 years of age
- Inactive anterior uveitis
- Active intermediate or posterior inflammation (involvement of vitreous, choroid or retina)
- Participants who have received antiviral therapy <14 days prior to enrolment
- Participants who have received periocular or intraocular corticosteroid injection <8 weeks prior to enrolment
- Current use of oral corticosteroids
- Immunocompromised participants (primary or secondary immunodeficiency disorders)
- Prior immunosuppressive therapy in the past 3 months
- Directed PCR testing positive for HSV or VZV
- Plans to conceive during the study period, pregnant or breastfeeding mothers (blood or urine pregnancy test for all females of childbearing age is mandatory within 4 weeks prior to enrolment)
- Complete blood count with white blood cell, absolute neutrophil or platelet count lower than the lower limit of reference laboratory normal
- Blood urea nitrogen or creatinine above the upper limit of reference laboratory normal
- Recent ocular surgery within the past 30 days or planned surgery within the next 45 days
- Systemic autoimmune disease or ocular condition (besides anterior uveitis) anticipated to dictate or alter treatment course

In Trial II, participants will be excluded if

- They have not had prior positive CMV by nucleic acid amplification test (e.g., polymerase chain reaction) of aqueous humor obtained via anterior chamber paracentesis during active flare of inflammation (uveitis)
- Have active inflammation
- Did not have a 2-week period of no antiviral (treatment) prior to randomization to long-term prophylaxis

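### Patients may enter Trial II directly, but the Trial II eligibility lists carry over almost none of Trial I's safety and confounder criteria and no baseline pregnancy or HIV test is scheduled for them

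*Protocol*

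**What the plan says.** Protocol section 4.1 opens a second route into Trial II: "Additionally, patients with known CMV anterior uveitis, but who are inactive, may enter Trial II directly". SAP section 2.1 repeats it. Protocol section 7.1.3 is consistent with this, since it provides for trial consent at Trial II Exam 1 for new participants.

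Section 5.1 introduces its longer list with "In order to be eligible to participate in Trial I of this study, an individual must meet all of the following criteria". That list includes "Participant willingness to use an acceptable method of contraception during the study period", adult age, understanding of the study and commitment to follow-up. Trial II then gets its own list of three inclusions: a history of CMV positivity, at least 2 weeks of inactivity, and "Have a period of 2 weeks of no antiviral prior to long-term treatment initiation".

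Section 5.2 puts 15 exclusions under a Trial I subheading. They cover, among others, pregnancy, breastfeeding and plans to conceive, immunodeficiency, steroids by several routes, immunosuppression, blood counts and renal function, and "Recent ocular surgery within the past 30 days or planned surgery within the next 45 days". The Trial II list follows ("In Trial II, participants will be excluded if") with three items that mirror its inclusions, ending with "Did not have a 2-week period of no antiviral (treatment) prior to randomization to long-term prophylaxis". SAP section 5.2 only refers back to protocol section 5.

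Section 2.3.1 counts "infertility, teratogenesis, and carcinogenesis" among the rare risks of oral valganciclovir. It also says that pre-study laboratory tests identify high-risk patients, who are then excluded as the protocol specifies.

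**The concern.** A patient who enters Trial II directly never passes the Trial I list, so the Trial II list is the only written filter. A site following it literally could randomise a direct entrant who is pregnant or planning a pregnancy, is immunocompromised, or is quiet only because of an oral or recent injected steroid. Section 2.3.1 promises a safeguard that sections 5.1 and 5.2 do not supply for this group.

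Two things are at stake. The first is participant safety, over treatment of up to 12 months. The second, and lesser, is the Trial II primary endpoint. It is anterior chamber cell of at least 1+ at any study visit (SAP section 6.1), with no requirement that CMV be confirmed, so steroids, immunosuppression and ocular surgery could move it for reasons unrelated to the study drugs.

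**Working it through.** **Comparing the lists.**

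- Trial I has 15 exclusions. Four are laboratory-based: CMV PCR, HSV/VZV PCR, blood counts, and urea nitrogen or creatinine. That leaves 15 − 4 = 11.
- Of those 11, one carries over (the antiviral-free period) and one is reversed by design (inactive disease). 11 − 2 = 9 are absent from Trial II: age, active intermediate or posterior inflammation, periocular or intraocular steroid, oral steroid, immunodeficiency, immunosuppression, pregnancy and related items, ocular surgery, and confounding autoimmune or ocular disease.
- The count is 8 if Trial II's exclusion of active inflammation is read to include intermediate or posterior disease.
- The blood count and renal exclusions are absent too, as is the contraception inclusion.

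**Could the long list be study-wide?** The opening sentence of section 5.2 does speak of the study as a whole. But the long list excludes inactive anterior uveitis, which is the state Trial II requires. It can only be a Trial I list.

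**Do the procedures fill the gap?**

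- Section 7.1.2 ties the baseline blood, pregnancy and HIV tests to the interval between Exam 0 and randomisation. Trial II has no Exam 0.
- The laboratory row of the Schedule of Activities (section 1.2) is marked at Trial I Exams 0, 2 and 3 and at Trial II Exams 2-7 and 8. It is not marked at Trial II Exam 1. The first marked Trial II visit is at 1 month.
- The Baseline History Form is scheduled only at Trial I Exam 1, so no specified form records a direct entrant's steroid, immunosuppression or surgical history.
- An eligibility form is scheduled at Trial II Exam 1, but it can only check criteria that the protocol states.

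**Size of the endpoint effect.**

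The inputs come from SAP section 3.3: 28 per arm (105 × 0.8 / 3 = 28), risks of 25% and 65%, two-sided alpha 0.025, two-sample z-test.

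Power = Φ[(d − z·s0)/s1], with z = 2.2414, s0 = √(2·p̄(1−p̄)/n) and s1 = √((p1(1−p1)+p2(1−p2))/n).

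- Plan as stated: d = 0.40, p̄ = 0.45, s0 = 0.1330, s1 = 0.1217. (0.40 − 0.2980)/0.1217 = 0.838, so power is 79.9%. The SAP's 80% reproduces.
- Illustration: suppose 20% of Trial II participants are direct entrants and 20% of those take steroids or immunosuppression that halves their recurrence risk. Both shares and the halving are assumptions; the documents give no figures. The affected share is 0.20 × 0.20 = 4%, and each arm's risk is multiplied by 1 − 0.5 × 0.04 = 0.98. The risks become 24.5% and 63.7%, and d = 0.392. (0.392 − 0.2974)/0.1219 = 0.776, so power is 78.1%, a loss of about 2 points.
- Range over the affected share of all participants, same formula: 10% gives 75%, 20% gives 71%, 30% gives 66%.

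**The case against.** The strongest reply is that the gap concerns only direct entrants, and that safeguards exist.

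Roll-over participants met the Trial I criteria before re-randomisation. Their contraception and conception criteria are worded over the study period, which can be read to extend into Trial II. Trial II Exam 1 has an eligibility form and consent, and laboratory monitoring starts at 1 month in a schedule row that names pregnancy. Treatment for 12 months is a maximum, because participants exit at recurrence. All of this stands and narrows the point, but none of it gives a direct entrant a stated criterion or a baseline test.

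A reader might infer three stronger conclusions that the documents do not support.

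- **A large loss of power.** The 66% above needs 30% of all Trial II participants to be affected. Likewise, if 15% of everyone reached 1+ cell for a non-CMV reason, power would be 63%. Both apply assumed shares to roll-overs who had already been screened, and the sample size counts no direct entrants at all. The Trial I surgery criterion looks back 30 days and ahead 45, so restoring it would leave most surgery over 12 months untouched.
- **A biased endpoint.** Allocation is randomised 1:1:1 within site and outcome assessors are masked, so affected patients fall across arms by chance. Aim 2b separates CMV-positive from sterile recurrences, though only as a secondary analysis. The SAP's sensitivity analyses allow adjustment for chance imbalance, including in prior prednisolone use.
- **A changed scientific question, because immunodeficient hosts are let in.** The resistance rationale in protocol section 8.2 and SAP section 3.3 also names immunologically privileged organs such as the eye, so it does not rest on immunodeficient participants.

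**Conclusion.** The point holds for direct entrants and should be fixed before any are randomised. The written Trial II criteria would admit patients whom the sponsor's own Trial I criteria exclude on safety grounds, and section 2.3.1 promises an exclusion that is not specified for them. This rests on the text alone and needs no numerical assumption.

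The endpoint consequence is secondary: dilution or chance imbalance, not systematic bias. Its size depends on the number of direct entrants and the share affected, neither of which is given. About 2 points of power is one plausible value under the stated assumptions, and a large loss is not established. For roll-overs the weakness is smaller: no re-check is specified if their status changed during Trial I.

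**What to change.** Reconcile protocol sections 1.2, 2.3.1, 4.1, 5.1, 5.2, 7.1.2 and 7.1.3:

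- State in 5.1 and 5.2 that the sponsor's own Trial I safety and confounder criteria, all except those requiring active disease, also apply at Trial II entry.
- Check them on the Trial II Exam 1 eligibility form for direct entrants, and re-check current status for roll-overs.
- State which baseline tests and history form apply to direct entrants, and at which visit, so that section 2.3.1 agrees with the schedule.
- Leave it to the sponsor to decide whether any time window, such as the surgery window, needs adapting to a 12-month trial.

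The cost is protocol wording, a longer eligibility form and a few direct entrants becoming ineligible. The planned sample size is not affected, since it is built on 105 participants from Trial I.

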5.3 Strategies for Recruitment and Retention

The investigating ophthalmologist is conducting the search for potential participants by reviewing results of the nucleic acid amplification test (e.g., polymerase chain reaction) performed on aqueous fluid obtained from anterior chamber paracentesis. He or she will then determine if the patient meets all non-laboratory eligibility criteria. If so, the patient will be approached and participation in the study will be discussed. If consent is obtained, the patient will be formally enrolled into the study and randomized to one of the 3 treatment groups by the study coordinator. These patients will be coming from the study sites' patient population, including patients referred for evaluation of a possible infectious cause of their uveitis.

Participants enrolled in Trial I, if willing, will get re-randomized to one of 3 arms in Trial II and

stay on that suppressive therapy for 12 months.

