7.2.4 MEDICATION CESSATION

In the event of a serious adverse event, all study medications should be stopped and the medical monitor should be informed via a protocol deviation form. Further medical management will be at the discretion of the treating ophthalmologist and any consulting services. These patients should continue with scheduled study visits if possible.

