For both trials, individuals will be randomized to the three arms in a 1:1:1 ratio. Randomization will be stratified by site. Stratified, block randomization will ensure that an approximately equal number of patients are randomized to each treatment arm by site. UCSF biostatistician will prepare the randomization and it will be implemented in REDCap.

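### Trial II entry criteria do not carry out the protocol's own statement that participants with blood or renal abnormalities leave the study, so someone stopped for a laboratory SAE in Trial I can be re-randomised

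*Protocol*

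**What the plan says.** **The stated protection.** Protocol 2.3.1 describes how medication risk is kept down. On pre-study laboratory tests it says: "Patients identified as being high risk will be excluded from the study, as specified in our protocol". Shortly afterwards it makes a separate statement about on-study monitoring: participants who develop the blood or renal abnormalities specified in the protocol are taken out of the study.

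**What happens on an SAE.** Section 7.2.3 counts certain creatinine, leukocyte, platelet and haemoglobin values as SAEs. Section 7.2.4 then applies: "In the event of a serious adverse event, all study medications should be stopped". It adds that these patients should keep attending visits where possible. It does not say how long the stop lasts or mention Trial II.

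**How a participant reaches Trial II.** Section 5.3: "Participants enrolled in Trial I, if willing, will get re-randomized to one of 3 arms in Trial II". The same sentence sets the length of that treatment at 12 months. The randomisation paragraph after 8.2: "For both trials, individuals will be randomized to the three arms in a 1:1:1 ratio". One of the three Trial II regimens in 4.1 is "Group 1: Valganciclovir tablets 450 mg PO BID (2 tablets daily) and Placebo drops 1 drop BID".

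**Who may enter Trial II.** Sections 5.1 and 5.2 list three inclusion and three exclusion criteria. They cover a past CMV-positive aqueous sample, inactive inflammation, and two weeks without antivirals; the last exclusion reads "Did not have a 2-week period of no antiviral (treatment) prior to randomization to long-term prophylaxis". The blood-count, urea and creatinine exclusions appear under Trial I only.

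**Laboratory schedule.** Section 7.1.1 and the Schedule of Activities place laboratory tests at Trial I Exams 0, 2 and 3, and in Trial II from Exam 2 onward. None is marked at Trial II Exam 1, the re-randomisation visit.

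**The concern.** The risk section tells an ethics committee or a DSMC that participants who develop specified blood or renal toxicity do not continue. The people who enrol into Trial II work from section 5, and nothing there stops them re-randomising such a participant. The two-week antiviral-free condition does not help: time off drug after an SAE stop counts toward it.

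At stake is re-exposure to an antiviral, for up to a year, of someone whose drug was stopped for a laboratory SAE. The assignment would be masked to the study ophthalmologist, and the first scheduled Trial II laboratory check comes one month into dosing (Exam 2).

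**Working it through.** **1. The passages side by side, for a participant with a laboratory SAE in Trial I**

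| Question | Section | Answer in the text |
|---|---|---|
| Is study drug stopped? | 7.2.4 | Yes |
| Does the participant leave the study? | 2.3.1 | Yes, for specified blood or renal abnormalities |
| Does the participant leave the study? | 7.2.4 | No; visits continue if possible |
| Does the stop extend to Trial II? | 7.2.4 | Not stated |
| Does a Trial II criterion refer to the SAE, the stop, blood counts or renal function? | 5.1, 5.2 | No |
| Is there a laboratory test at re-randomisation? | 7.1.1, Schedule of Activities | No |
| May the participant be re-randomised? | 5.3 | Yes, if willing |

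Once the eye is inactive and two weeks have passed without antivirals, every listed Trial II criterion is met. Only the narrative sentence in 2.3.1 points the other way. That sentence does not say which abnormalities it means. Sections 7.2.1 and 7.2.3 both specify laboratory values, and 7.2.2 handles the non-serious ones by dose reduction rather than removal. I therefore rest the point on the SAE-level values.

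**2. Chance of oral drug.** Under 1:1:1 allocation it is 1/(1+1+1) = 1/3, and the chance of either active antiviral is 2/3. If k stopped participants enter, the chance that at least one is assigned oral drug is 1 − (2/3)^k: 33% for k = 1, 56% for k = 2, 70% for k = 3.

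**3. Number affected.** The documents give no stop rate, so I assume 2% to 10% of the 117/3 = 39 oral participants in Trial I, all of whom become quiescent, agree and roll over.

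- Stopped: 39 × 0.02 = 0.8 to 39 × 0.10 = 3.9.
- Re-randomised to oral drug: 0.78/3 = 0.3 to 3.9/3 = 1.3.

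This counts re-exposure to oral drug only. Participants stopped while on drops or placebo would be additional entrants, but not re-exposures to oral drug.

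**4. Effect on the Trial II contrast.** At the upper end, 1.3 of 35 participants per arm is 3.7%. If their treatment effect were lost entirely, the SAP's 40-point design difference would shrink by 0.037 × 40 = 1.5 points.

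**5. Power cost of tighter eligibility.** First, the plan's own figure (SAP 3.3): 105/3 = 35 per arm, and 35 × 0.80 = 28 evaluable. For 25% versus 65% at two-sided alpha 0.025, with the pooled-variance z-test:

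z = (0.40 × √28 − 2.241 × √(2 × 0.45 × 0.55)) / √(0.25 × 0.75 + 0.65 × 0.35) = (2.117 − 1.577)/0.644 = 0.838, so power is 79.9%, against the stated 80%.

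If an added criterion kept some of the 105 out (assumed shares):

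| Excluded | Evaluable per arm | Power |
|---|---|---|
| 0% | 28.0 | 79.9% |
| 1% | 27.7 | 79.4% |
| 2% | 27.4 | 78.9% |
| 5% | 26.6 | 77.5% |
| 10% | 25.2 | 74.8% |

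I used the SAP's 40 points. The 36 points in Protocol 8.2 does not reproduce at alpha 0.025 (power 69.7%), which is a separate matter.

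**The case against.** The strongest reply is that Trials I and II form one sequential study, so being taken out of the study under 2.3.1 already bars Trial II. That is a fair reading of the sentence, and it means that continued eligibility is a feature of section 5 and not of the whole protocol. It does not settle the matter, because 7.2.4 keeps the same participants on visits and the criteria that sites apply do not repeat the bar.

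A second reply is that an investigator would notice. Masking does not hide an SAE: under 7.2.5 the investigator writes its summary, the medical monitor judges relatedness, and the investigator may stop drug thought to be the cause. An eligibility form is also due at Trial II Exam 1. This lowers the likelihood of harm, but none of these steps is tied to Trial II entry, and section 5 lists no discretionary safety exclusion.

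A reader might also infer more than the documents support:

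- *That re-randomisation contradicts the cessation rule.* Section 7.2.4 is silent on restart and on Trial II. This is a gap, not a contradiction.
- *That it breaks the exclusion of high-risk patients.* That sentence in 2.3.1 follows from the pre-study laboratory tests and concerns screening.
- *That anyone stopped has been shown to be intolerant.* The SAE list includes hospitalisation for any cause, cancer and seizure, and the participant may have been on placebo.
- *That the intention-to-treat comparison is materially diluted.* On the figures above it is not.

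**Conclusion.** The point holds as an inconsistency between a stated protection and the sections that should deliver it. Section 2.3.1 takes participants with specified blood or renal abnormalities out of the study; 7.2.4 and the Trial II criteria do not. As written, a participant stopped for a laboratory SAE in Trial I can meet every Trial II entry criterion, with a 1/3 chance of oral valganciclovir. Twelve months is the maximum exposure, since participants exit at recurrence.

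The expected number re-exposed to oral drug is about 0.3 to 1.3. That rests on an assumed 2% to 10% stop rate and on every stopped participant rolling over, so it leans high for any given rate. The reason to act is participant safety. There is no material threat to bias or power.

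**What to change.** Reconcile Protocol 2.3.1, 5.1 and 5.2 (Trial II), 5.3, 7.1.1 and 7.2.4. The Trial II eligibility criteria should state how a Trial I SAE stop, or a specified blood or renal abnormality, affects re-randomisation. Section 7.2.4 should say whether its stop extends to Trial II, and 2.3.1 should point to the values it means. The Trial I Exam 2 and 3 laboratory results and the adverse event log are already collected and can support the check. The clinical criterion is for the investigators to set.

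Two extensions are better left out. Applying the rule to any unresolved laboratory abnormality would cut across 7.2.2, which handles non-serious ones by dose reduction. Making the medical monitor the gatekeeper would go beyond SAP 6.5, which lets the monitor request unmasking after an adverse event but gives no eligibility role.

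The cost is a short amendment and at most a few fewer Trial II entrants: about one percentage point of power if 2% of the 105 are excluded.
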